6.1 Information to be collected on screening failures

Patients may discontinue from the study from Visit 8/8A through Visit 9, prior to any open-label medication being administered.

Patients discontinuing prior to first infusion in the Extension study are considered screening failures.

If a patient discontinues before entering the open-label treatment period, the demographic information, reason for non-eligibility and screening log should be completed on the eCRF.

6.2 Patient demographics/other baseline characteristics

Group 1: Baseline demographical information for continuing patients was collected at the beginning of the Core study and will not be collected again in the Extension study. Visit 1 of the Core study will be considered as Baseline 1. Any adverse events that occur after Visit 8 of the Core study but prior to the first dose of the Extension study (Visit 9) will be also collected on the adverse event eCRF.

Group 2: Baseline demographical information, medical history, concomitant medications, physical exam and laboratory/imaging assessments will be collected at Screening visit (Visit 8A) or Visit 9; this will be considered as Baseline 2.

6.3 Treatment exposure and compliance

Concomitant Medications/Non-drug therapy prior to the first dose of study medication in the Extension study and after start of study drug will be collected, including medication name and reason. More details (including dose and dates of intake) will be provided for the following categories of treatments: osteoporosis-related medications, nutritional supplements (vitamin D/ calcium), and GCs. A Dosage Administration Record will be completed for each i.v. dose of zoledronic acid. Information collected will include the date of dose, start and stop times of infusion and the reason for each dose.

Compliance with vitamin D/calcium will be assessed by the investigator and/or study personnel at each visit using information on diet and supplement use provided by the patient/caregiver. This information should be captured in the source document, at each visit, and in the Concomitant Medication/Non-significant therapy eCRF. All study treatment and any additional treatment (i.e. vitamin D and/or calcium provided by Novartis or designee) dispensed and returned must be recorded in the Drug accountability log.

6.4 Efficacy

The efficacy variables will be measured using the following techniques:

- vertebral morphometric fractures

- DXA measurements
- bone marker analysis

- bone age and metacarpal cortical width assessment
- pain assessment

6.4.1 Vertebral morphometric fractures

Group 2 only:

At Visit 8A, anterior-posterior (AP) and lateral X-rays of the lumbar and thoracic spine will be taken to evaluate the presence of vertebral fractures of Genant grade 1 or higher or radiographic signs of vertebral compression fracture. AP spine X-ray will be employed at baseline, in order to identify fractures that may not be readily visualized on the lateral spine because of rotation/scoliosis/other.

Radiographic signs of fracture include loss of endplate parallelism, vertebral buckling and endplate interruption. Patient's eligibility must be confirmed by the central imaging laboratory before the patient can be enrolled. AP and lateral thoracolumbar spine X-rays taken within 1 month of Visit 8A (screening) can be used. The film and report must be sent to central imaging for fracture confirmation.

All patients:

[figure not shown]
Lateral thoraco-lumbar spine X-ray will be performed at the final visit of the Extension study (Visit 15) to assess incident vertebral fractures. Vertebral fractures present at baseline or occurring during the study will be defined according to the Semi-Quantitative (SQ) method and confirmed with the Quantitative Morphometric (QM) method for vertebral fracture assessment:

1. A mild (Grade 1) vertebral fracture is defined as greater than or equal to (\geq)20% and less than or equal to (\leq) 25% reduction in anterior, middle, and/or posterior vertebral height.
2. A moderate (Grade 2) vertebral fracture is defined as greater than ($>$) 25% and less than or equal to (\leq) 40% reduction in any vertebral height.
3. A severe (Grade 3) vertebral fracture is defined as greater than ($>$) 40% reduction in any vertebral height.

or based on radiographic signs of fracture, including: loss of endplate parallelism, vertebral buckling and endplate disruption.

Specific instructions for sending radiographic images will be distributed to investigators prior to the start of study.

Vertebral morphometry (or concave index) will be calculated using the average ratio between mid-height and posterior height from the first to the fourth lumbar vertebrae (L1 to L4) ([Land et al 2006b](#))

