monitoring and contraception in girls of child bearing potential. A maximum dose of 5 mg zoledronic acid (regardless of patient weight) and a minimum 30 minute infusion time 6 monthly are designed to reduce the risk of possible adverse effects. This dose regimen has been used in children with primary and secondary osteoporosis and has shown a favorable risk-benefit profile.

4 Population

Group 1: Patients who have received at least one dose of study drug, have completed participation in the Core study and who meet the inclusion/exclusion criteria for this extension, will be eligible to participate. These patients have been previously diagnosed with non-malignant conditions (including but not limited to rheumatologic conditions, IBD, DMD, nephrotic syndrome) and have been treated with systemic GCs (i.v. or oral) prior to the Core study and have evidence of at least 1 vertebral compression fracture confirmed by central reading or one or more low-trauma lower extremity long bone fractures or two or more low trauma upper extremity long bone fractures confirmed by radiology report.

Group 2: Patients who were not eligible for the Core study because of clinically significant back pain from vertebral fracture and the preexisting clinical care at the Investigator's site is to treat this type of patient with a bisphosphonate.

Approximately 100 patients will be eligible for enrollment into the extension, for both groups. Patient recruitment in Group 2 will stop once enrollment in the Core study is completed

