4.1 Inclusion criteria

Patients eligible for inclusion in this study have to fulfill all of the following criteria:

- Written informed consent must be obtained before any assessment is performed. An assent needs to be provided in accordance with ICH and local regulations.

Group 1:

1. Children and adolescents, male or female, between 6 to 19 years of age who met the inclusion criteria for entry into the Core study and who took at least one dose of study drug and have completed Visit 8 of the CZOL446H2337 Core study.
2. Patient must be enrolled into the extension at Visit 9 up to 10 months after Visit 5 (month 6) of the Core study.
3. Patients who followed the regimen of calcium and vitamin D intake as required in the Core study (at least 1000 mg calcium for 6-8 years of age or at least 1300 mg calcium for 9-19 years of age and at least 600 IU daily vitamin D, through diet or supplementation).

Group 2:

1. Children and adolescents, male or female, between 5 to 17 years of age who met the inclusion criteria for entry into the Core study but were not enrolled because of clinically significant back pain from vertebral fracture and the preexisting clinical care at the Investigator's site is to treat this type of patient with a bisphosphonate.
2. Confirmed diagnosis of non-malignant conditions (including but not limited to rheumatic conditions, inflammatory bowel disease, Duchenne muscular dystrophy, nephrotic syndrome) who have stable normal renal function for at least 3 months prior to screening or

other subtype of secondary osteoporosis in children taking GCs, except patients with oncologic conditions (such as lymphoma and leukemia) see [Appendix 6](#)), treated with systemic GCs (i.v. or oral) within the 12 months preceding enrollment in the study (any duration)

3. Lumbar Spine areal BMD Z-score of - 0.5 or worse confirmed by central imaging
4. Evidence of at least 1 vertebral compression fracture (at least Genant Grade 1 vertebral compression or radiographic signs of vertebral compression*) seen on X-ray within 1 month of or at screening visit confirmed by central reading.

*Radiographic signs of vertebral compression fracture include loss of endplate parallelism, vertebral buckling and endplate interruption.

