Group 1: change in BMC at the lumbar spine and total body at Months 18 and 24 relative to both baselines between zoledronic acid and placebo will be evaluated using an ANCOVA model with treatment, pooled center, underlying condition treated with GCs and baseline BMC (Visit 1 of Core study) as explanatory variables. The 2-sided 95% confidence intervals for the difference in least squares means between zoledronic acid and placebo will be provided.

Group 2: change from Baseline 2 (Visit 8A/9) in BMC at the lumbar spine and total body at Months 18 and 24 in zoledronic acid group will be presented.

9.5.1.3 Relative change in biochemical markers of bone turnover (Serum NTX, TRAP-5b, BSAP and P1NP)

Group 1: a transformation of the log ratio of treatment value vs. baseline value (calculated by dividing the post-baseline value by the baseline value and then applying the \log_e transformation) at each visit will be used to normalize the distribution of the biochemical marker parameters. An ANCOVA model with treatment group, pooled center, underlying condition treated with GCs, and \log_e (baseline value), as explanatory variables will be performed on the transformed data at each post-baseline time point.

The 2-sided 95% confidence intervals for the difference in least squares means of transformed data between zoledronic acid and placebo will be provided using the described ANCOVA model and then back transformed to the original scale.

Group 2: summary statistics and relative change from Baseline 2 (Visit 8A/9) of biochemical markers of bone turnover will be presented.

9.5.1.4 Incidence of new clinical vertebral fractures and new morphometric vertebral fractures during the 12 month extension period

Group 1: The number and percentage of patients with new vertebral fractures and new morphometric vertebral fractures during the 12 month extension period will be presented by

Core treatment group. Between-treatment differences will be evaluated using Fisher's exact test. A new morphometric vertebral fractures during the 12 month extension period is defined as a morphometric vertebral fracture present at Month 24 X-ray which is not present at the extension baseline (Core Visit 8 and Visit 1 X-rays).

Group 2: number and percentage of patients with new vertebral fractures and new morphometric vertebral fractures during the 12 month extension period will be presented.

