### General considerations

#### Baseline definition

Unless otherwise specified, the following general rules will be applied for defining baseline.

- Core baseline: core baseline is defined as the last non-missing measurement on or prior to the date of first study drug infusion in core study.

- Extension baseline: extension baseline is defined as the last non-missing measurement on or prior to the date of first study drug infusion in the extension study. If no extension assessments are available on or prior to the first drug infusion in the extension study, the last assessment in core study will be used instead.

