The number and percentage of patients with new vertebral fractures and new morphometric vertebral fractures during the 12 month extension period will be presented by core treatment group. Between-treatment differences will be evaluated using Fisher's exact test. New vertebral fractures are defined as fractures of Genant grade 1 or higher that occur at lumbar or thoracic spine from first extension dose infusion to the end of the extension study. New morphometric vertebral fractures during the 12 month extension period is defined as a morphometric vertebral fracture present at Month 24 X-ray which is not present at extension baseline.

- **Change in 2nd metacarpal cortical width at Month 24 relative to baseline, zoledronic acid group vs. placebo**

The change in 2nd metacarpal cortical width at Month 24 relative to core baseline will be evaluated using an ANCOVA model with core treatment, pooled center, underlying condition treated with glucocorticoids and core baseline bone age as explanatory variables and pooled centers as random effect.

From the model, core treatment difference in least squares means between zoledronic acid group vs. placebo group will be estimated and presented together with two-sided 95% CI and p-value. In the same table, the LS means and standard errors for change from baseline in 2nd metacarpal cortical width at Month 24 will be presented for each core treatment group. Descriptive statistics will also be shown for baseline and Month 24 visits.

[figure not shown]
Above analysis will be carried out with respect to both baselines (core baseline as well as extension baseline).

[figure not shown]
- **Reduction in pain from baseline, zoledronic acid group vs. placebo**

[figure not shown]
Pain is assessed using Faces Pain Scale-Revised (FPS-R) at first infusion in the extension study (Visit 9), Month 15, 18, 21 and 24, which ranges from 0 (No Pain) to 10 (Very Much Pain). Details of FPS-R can be found in Appendix section “Faces Pain Scale” in the protocol.

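### Two SAP rules for new fractures in Group 1 differ from the protocol without explanation: one leaves out sign-only fractures, the other no longer names the Core Visit 1 film

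*Protocol*

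**What the plan says.** **What counts as a fracture.** Protocol 6.4.1, in the part that applies to all patients, sets one definition for two time points: "Vertebral fractures present at baseline or occurring during the study will be defined according to the Semi-Quantitative (SQ) method", with confirmation by quantitative morphometry. It lists Grades 1 to 3 by height loss, starting at 20%, and then adds an alternative route: "or based on radiographic signs of fracture, including: loss of endplate parallelism, vertebral buckling and endplate disruption".

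The SAP (Analysis for efficacy variables) is narrower for one of its two fracture endpoints: "New vertebral fractures are defined as fractures of Genant grade 1 or higher that occur at lumbar or thoracic spine". It does not mention radiographic signs. Its other endpoint, new morphometric vertebral fractures, carries no grade limit.

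**What counts as new.** Protocol 9.5.1.4 requires a morphometric fracture on the Month 24 film "which is not present at the extension baseline (Core Visit 8 and Visit 1 X-rays"). The SAP requires "a morphometric vertebral fracture present at Month 24 X-ray which is not present at extension baseline" and does not list the films. Its Baseline definition section says, as a general rule that holds unless otherwise specified, that "extension baseline is defined as the last non-missing measurement on or prior to the date of first study drug infusion in the extension study".

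**How the endpoints are used.** New clinical and new morphometric vertebral fractures are Group 1 secondary objectives 4 and 5 (protocol 2.2). Both documents compare the core treatment groups by Fisher's exact test, with hypothesis tests at the 0.05 level. The SAP's analysis sets contain only patients who completed the Core study, which is Group 1.

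**The concern.** The SAP does not say that it changes either rule, and it gives no reason for doing so. The first difference makes an endpoint narrower than the protocol's definition. A vertebra with new endplate disruption and less than 20% height loss is a fracture under protocol 6.4.1, but not a new vertebral fracture in the SAP. The second makes an endpoint wider: an earlier fracture that was not read at Visit 8 can come back as a new one.

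At stake is the classification of individual children in secondary endpoints where events are likely to be few. About 100 patients are planned over both groups (protocol 9.6), so the two core arms of Group 1 together are at most about that size. Two programmers, one working from the protocol and one from the SAP, could produce different counts from the same central readings.

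**Working it through.** The plan gives no fracture rate, effect size or power, so there is no planned figure to reproduce. The check compares the definitions and then shows how sensitive the test is.

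**Step 1: which incident findings count as a new vertebral fracture.**

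| Incident finding | Protocol 6.4.1 | SAP, new vertebral fracture |
|---|---|---|
| Grade 1 or higher | fracture | counted |
| Radiographic signs, below Grade 1 | fracture | not counted |
| Neither | no fracture | not counted |

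The rules differ in the second row only. Because the SAP's morphometric endpoint has no grade limit, the same finding could still be counted there if 6.4.1 is applied.

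**Step 2: which histories count as a new morphometric fracture.** Write the readings of a vertebra as (Visit 1, Visit 8, Month 24), with 1 for fracture read and 0 for not read. This gives 2 × 2 × 2 = 8 histories. I read the protocol's parenthesis as requiring absence from each of the two named films. Table 6-1 schedules Group 1 X-rays at Visits 8 and 15, so the last film before the first extension infusion is normally Visit 8.

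- Protocol: new only for (0,0,1).
- SAP under its general baseline rule: new for (0,0,1) and (1,0,1).
- The other six histories are not new under either rule. In particular, (1,1,1), an old fracture still visible at Visit 8, is never counted.

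The rules differ in one history of eight. That is a count of patterns and not a probability. The pattern needs discordant readings or a vertebra that has reshaped by Visit 8.

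**Step 3: what one child can do to the test.** Assumptions, since the documents give none: equal core arms of 30, 40 or 45 children, a two-sided Fisher's exact test (the SAP does not state sidedness), and the event counts shown.

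| Events by arm | 30 per arm | 40 per arm | 45 per arm |
|---|---|---|---|
| 0 vs 5 | 0.052 | 0.055 | 0.056 |
| 0 vs 6 | 0.024 | 0.026 | 0.026 |
| 1 vs 6 | 0.103 | 0.108 | 0.110 |
| 1 vs 5 | 0.19 | 0.20 | 0.20 |
| 2 vs 4 | 0.67 | 0.68 | 0.68 |

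One child added to the empty arm (0 vs 6 to 1 vs 6), or one removed from the other arm (0 vs 6 to 0 vs 5), moves the result across 0.05 at all three sizes. These counts were chosen to show the sensitivity. In the last two rows the p-value changes a good deal but stays above 0.05 throughout.

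**The case against.** The strongest reply has four parts.

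**The Genant limit may be deliberate.** Section 6.4.1 is headed morphometric fractures, while the SAP's new vertebral fractures appear to serve the clinical-fracture objective. Neither document as supplied defines a clinical vertebral fracture, and part of the protocol's efficacy section is redacted. This stands as a reason for caution: it cannot be said that new fractures are undercounted overall. It does not remove the conflict, because 6.4.1 states its definition for fractures occurring during the study in general and the SAP does not explain the narrower rule.

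**The baseline difference may be only wording.** Protocol 9.5.1.4 itself uses the term extension baseline and glosses it with the two films, and the SAP's general rule yields where something else is specified. This partly stands: the SAP could be read as carrying the protocol's meaning. But the SAP's fracture paragraph specifies nothing else, so its own general rule applies.

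**The effect is small and unmeasured.** This stands. The morphometric difference needs one specific history, gradings are confirmed by quantitative morphometry, and these are secondary comparisons in an extension whose primary objective is descriptive safety.

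**Stronger readings are tempting but not supported.**

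- A reader might infer that a sign-only finding admits a child to the analysed population and then cannot count at follow-up. The entry criterion that says so, "at least Genant Grade 1 vertebral compression or radiographic signs of vertebral compression", is for Group 2, which the SAP does not analyse. For Group 1, Section 4 of the protocol says only that patients "have evidence of at least 1 vertebral compression fracture confirmed by central reading" or have qualifying long-bone fractures. It does not mention signs, and the Core protocol is not among the documents.
- A reader might extend the Visit 1 problem to Group 2. Those children have no Core films and no Fisher comparison, so it cannot arise there.
- A reader might fault both documents for not counting worsening of a vertebra already fractured. The stated objectives concern new fractures, so that is a possible addition and departs from neither document.

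**Conclusion.** The point holds for Group 1 as two separate, unexplained differences between the current SAP and the current protocol. One narrows the new vertebral fracture endpoint by leaving out sign-only fractures. The other can widen the new morphometric fracture endpoint by one history: fracture read at Visit 1, not at Visit 8, and again at Month 24. They act on different endpoints, so they should not be described as one endpoint biased in both directions.

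The number of children affected cannot be computed, because the documents give no rate for sign-only fractures or for discordant Visit 1 and Visit 8 readings. The p-values above show only that a single reclassification can matter under assumed arm sizes and event counts. The second difference also rests on applying the SAP's general baseline rule to the X-rays. The differences should be resolved before the analysis because the correction is cheap and removes a choice that would otherwise be made in programming.

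**What to change.** In the SAP's paragraph on incidence of new vertebral fractures:

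- **(a)** Define new vertebral fractures by the protocol 6.4.1 rule: Grade 1 or higher, or radiographic signs, centrally read. Show the grade-only count beside it as supportive, because signs are more subjective than height grades.
- **(b)** For new morphometric fractures, name the Core Visit 1 and Core Visit 8 X-rays as the reference films and require that the fracture is absent from both.

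If the sponsor intends either SAP rule as it stands, the SAP should say that it departs from the protocol and why.

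The cost is SAP wording and one supportive count. No additional X-rays are needed. Part (b) uses the Visit 1 readings that the protocol's own rule already presupposes.

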6.4.3 DXA measurements

DXA measurements of the lumbar spine (LS), total body and distal femur will be performed on all patients. LS- BMD Z-score, LS bone mineral content (BMC), Total body BMC [REDACTED] will be assessed at the final visit of the Core study (for Group 1) or Visit 8A-Screening Visit (for Group 2), Visit 9 (Month 18) and Visit 15 (Month 24) (final extension study visit/EOS). DXA will be acquired locally and the results will be sent to a central reader for evaluation.

Group 1: The DXA scans (hip, spine and distal femur) from Visit 8 will be used for the extension Visit 9 provided the DXAs have been obtained within 3 months of the Visit 9 infusion; otherwise, the DXA scans must be repeated at Visit 9.

Group 2: Lumbar Spine-BMD-Z score of -0.5 or worse at Visit 8A needs to be confirmed by central imaging vendor.

6.4.4 Bone marker analysis

Specialized serum tests for BSAP, P1NP, TRAP-5b and NTX will be performed. Blood will be drawn from patients at the final visit Core study (for Group 1) or Visit 9 (for Group 2), at Visit 12 (Month 18) and Visit 15 (Month 24) (final extension study visit/EOS). Detailed shipping instructions will be provided in the Investigator Laboratory Manual.

